12. PILOT PROJECT - COST-EFFECTIVENESS

We have performed a Markov model to compare differential cost of surveillance for advanced adenomas at 3 vs at 5 years ([name], unpublished data). Considering 15 years surveillance, the cost of a 3-year surveillance interval after high-risk adenoma removal would be 602.82 € per patient, whereas the cost with a 5-year surveillance interval would be 548.99 € per patient. That supposes a differential cost of 53.83 € per patient. In Europe, approximately 6.000.000 colonoscopies are performed every year, and in approximately 5% of them high-risk adenomas are diagnosed. Thus, the estimated cost saving of 53.83€ per patient would translate to a total saving of 16.149.000 € per year in Europe. Moreover, a reduction in the number of colonoscopies performed for polyp surveillance will also avoid possible complications for patients. The colonoscopy burden that is currently being used for performing surveillance colonoscopy could be more appropriately used for CRC screening.

13. TIME PLAN

- One year is allowed for planning and set-up of the study infrastructure.
- The approximate recruitment period necessary to include a sufficient number of patients will be 2 to 3 years, or longer if the number of participating countries/centres is lower than expected.
- Surveillance colonoscopies will be performed at years 3, 5 and 10 of follow-up. Main publication will be after 5 years and 10 years. The publications following analysis of the primary endpoint will be after 5 years and 10 years. A baseline manuscript documenting the quality control aspects of the colonoscopies will be prepared after all patients have been recruited.

14. Study organisation

PRINCIPAL INVESTIGATOR TEAM

ROLE: coordination of the study

MAIN PRINCIPAL INVESTIGATOR: [name]

CO-PRINCIPAL INVESTIGATOR: [name]

EPOS-III STUDY PI: [name]

GOVERNING BOARD:

ROLE: Set the main rules of the trial and national coordination of the study

Reviews and summarizes reports on quality and adverse events from the secretariat and interacts with the DSMB.

COMPOSITION: 1 delegate per participant country and a representative of Frontiers Science

SPAIN: [name] (Chairman of the Governing Board)

NORWAY: [name] (Co-Chair)

NETHERLANDS: [name]

SWEDEN: [name]

POLAND: [name],

PORTUGAL: [name]

AUSTRIA: [name]

DENMARK: [name]

FRONTIERS SCIENCE: [name]

SCIENTIFIC STUDY COMITEE

Tasks and responsibilities: Overall responsibility and decision authority for the trial in general, including aspects of management, screening, quality control, endpoint observation and publication activity. Join meetings of the Governing Board and the

Feb 11th 2017

Scientific Study Committee will be performed at least twice a year during the development of the study.

MEMBERS

[name], [name], [name], [name], [name], [name], [name], [name], [name], [name], [name], [name], [name], [name], [name], [name], [name]

DSMB: A 3-person group to investigate data after 5 years to decide on early termination of the study due to extreme differences between randomization arms will be designed in coming weeks

REFERENCES

1. GLOBOCAN Database. International Agency for Research on Cancer. World Health Organization, 2008. (Accessed at <http://globocan.iarc.fr/>.)

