Feb 11th 2017

EPoS
the European Polyp Surveillance trial group

PROTOCOL. Version Feb 11 2017

Amendments:

February 11th 2017

PROTOCOL SUMMARY AND SIGNIFICANCE

This protocol describes the epos (ancient Greek (Επος) for “story”) of a group of related clinical trials aiming at addressing one of the most important unsolved challenges in the prevention of colorectal cancer (one of our major cancer killers); the surveillance of patients with premalignant polyps in the large bowel.

This project is timely because large scale colorectal cancer screening programmes are currently rolled out in most Western countries. These programmes are diagnosing large numbers of individuals with premalignant polyps (adenomas and serrated polyps). This creates both a diagnostic and resource dilemma, because the optimal surveillance strategy for these individuals to reduce future cancer risk is currently unknown.

The EPoS trials will randomize or register more than 27,500 individuals in different European countries to different surveillance colonoscopy intervals to disentangle the most effective and cost-effective surveillance strategy for the population. Subjects will be randomized according to their presenting polyp characteristics

The EPoS I trial randomizes patients with low-risk adenomas into 5 or 10-year surveillance; EPoS II randomizes patients with high-risk adenomas into 3 or 5-yearly surveillance; EPoS III will include patients with serrated polyps in a one-arm study with surveillance after 5 and 10 years. The primary endpoint for all three trials is incidence of colorectal cancer after 10 years of follow-up.

This EPoS trials are the largest in polyp surveillance ever conducted. They address a clinical problem affecting hundreds of thousand individuals in Europe and the US each year, it has a large size, and should thus provide definitive results.

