4.3 SPECIFIC DESIGNS AND SETTINGS

4.3.1. EPoS I

Eligible individuals are persons with low-risk adenomas removed at baseline colonoscopy (1-2 tubular adenomas size <10mm with low-grade dysplasia) and no serrated polyps with dysplasia, with diameter 10 mm or larger at any location or with diameter 5 mm or larger proximal to the splenic flexure.

Individuals will be **randomized** into one of two intervention groups:

Group 1: Surveillance colonoscopy at 5 and 10 years after baseline colonoscopy.

Group 2: Surveillance colonoscopy at 10 years after baseline colonoscopy.

The primary and secondary endpoints will be analyzed directly after the 10 year surveillance colonoscopy, (figure 1).

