4.3.2 EPoS II

Eligible individuals are persons with high-risk adenomas removed at baseline colonoscopy (three to ten adenomas; or one or more adenoma w/size \geq 10mm, or one or more adenoma with high-grade dysplasia or villous growth pattern).

Individuals will be **randomized** into one of two intervention groups:

Group 1: Surveillance colonoscopy 3 and 5 years after baseline colonoscopy

Group 2: Surveillance colonoscopy 5 years after baseline colonoscopy

Feb 11th 2017

Individuals in both group 1 and group 2 will be subjected to a final colonoscopy surveillance after 10 years (figure 1).

The primary and secondary endpoints will be analysed directly after the 10 year surveillance colonoscopy, (figure 1). A secondary analysis will be performed after the 5 year colonoscopy.

For centers with current guidelines for 1 year surveillance for multiple or large (>20mm) adenomas; they may exclude those patients.

In both EPoS I and EPoS II, surveillance intervals after the first surveillance colonoscopy take into account findings at the first surveillance colonoscopy. Surveillance intervals after first surveillance colonoscopy are shown in **Figure 2A (EPoS I) and-B (EPoS II)**.

Figure 2. Surveillance intervals after first follow-up colonoscopy in EPoS I and II

Figure 2A: EPoS I

[figure not shown]
[figure not shown]

Figure 2B; EPoS II

LRA: Low risk adenoma; HRA: High-risk adenoma

Figure 2C: Polyp characteristics and eligibility in EPoS. SP: Serrated polyp, TSA: Traditional Serrated Adenoma.

Serrated polyp	≥10mm SP and/or SSA with dysplasia and/or TSA	≥5mm SP in the proximal colon	<10mm SP with no dysplasia in the distal colon	<5mm SP with no dysplasia in the proximal colon	None
No adenoma	EPoS III	EPoS III	No inclusion	No inclusion	No inclusion
1-2 tubular adenoma <10mm with low-grade dysplasia	EPoS III	EPoS III	EPoS I	EPoS I	EPoS I
>2 adenoma	EPoS II	EPoS II	EPoS II	EPoS II	EPoS II
Villous histology	EPoS II	EPoS II	EPoS II	EPoS II	EPoS II
High grade dysplasia	EPoS II	EPoS II	EPoS II	EPoS II	EPoS II
Adenoma ≥10mm	EPoS II	EPoS II	EPoS II	EPoS II	EPoS II

4.3.3. EPoS III;

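### The time plan puts primary-endpoint analysis and publication at 5 as well as 10 years; in EPoS I a by-arm CRC comparison soon after year 5 is biased towards the longer interval

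*Protocol*

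**What the plan says.** Section 13 (Time plan), in a bullet that covers all the trials together, states: "Main publication will be after 5 years and 10 years". It then adds: "The publications following analysis of the primary endpoint will be after 5 years and 10 years".

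Other sections give a single time:
- Protocol summary: "The primary endpoint for all three trials is incidence of colorectal cancer after 10 years of follow-up".
- Section 4.3.1, EPoS I: "The primary and secondary endpoints will be analyzed directly after the 10 year surveillance colonoscopy".
- Section 11.1: the margins of 0.5% (EPoS I) and 0.7% (EPoS II) apply to the absolute difference in cumulative CRC incidence at ten years.
- Section 4.3.2, EPoS II: primary and secondary endpoints are analysed after the 10-year colonoscopy. A further analysis after the 5-year colonoscopy is called secondary. Section 4.3.1 has no such sentence for EPoS I.

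The EPoS I arms are "Group 1: Surveillance colonoscopy at 5 and 10 years after baseline colonoscopy" and "Group 2: Surveillance colonoscopy at 10 years after baseline colonoscopy". In EPoS II the shorter-interval arm is "Group 1: Surveillance colonoscopy 3 and 5 years after baseline colonoscopy", and the other arm also has a 5-year colonoscopy.

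Section 14 describes a three-person DSMB "to investigate data after 5 years to decide on early termination of the study due to extreme differences between randomization arms".

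**The concern.** The protocol gives two answers to when the primary endpoint is analysed. A later analysis plan cannot settle this quietly, because the conflict lies within the protocol itself.

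The choice matters most in EPoS I. Both arms are managed identically until Group 1's 5-year colonoscopy. Immediately afterwards, Group 1's symptomless cancers have been found and counted. Those in Group 2 stay uncounted until they cause symptoms or until year 10. Polyps removed at year 5 have had no time to prevent cancers. A by-arm comparison at that point therefore measures detection, and it makes the 10-year interval look better than it is.

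A report of that kind could be read as support for the longer interval. Patients and centres know the schedule, so a published by-arm result could also change attendance or prompt off-protocol colonoscopy before Group 2's only planned examination. That effect is plausible but not quantified here. The DSMB's 5-year review of EPoS I meets the same detection imbalance if it looks at total CRC by arm.

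**Working it through.** **1. The plan's own sample size.** Inputs from section 11 (sample size) and Table 2: CRC risk p = 1% or 2%, margin Δ = 0.5 or 0.7 percentage points, power 90%, one-sided alpha 0.05, true rates equal.

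n per arm = (z₀.₉₅ + z₀.₉₀)² × 2p(1 − p) / Δ², with (1.645 + 1.282)² = 8.564 (unrounded z values).
- EPoS I: 8.564 × 0.0198 / 0.000025 = 6,782.6, so 6,783.
- EPoS II: 8.564 × 0.0392 / 0.000049 = 6,851.1, so 6,852.

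Both match. Every input is a 10-year quantity, so a 10-year-only analysis leaves these numbers as they are.

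**2. Who has been examined soon after year 5.**

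| Trial | Shorter-interval arm | Longer-interval arm |
|---|---|---|
| EPoS I | 5-year colonoscopy done | none since baseline |
| EPoS II | 3- and 5-year colonoscopies done | 5-year colonoscopy done |

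The one-sided examination is specific to EPoS I.

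**3. First illustration, EPoS I, no true difference.** Assumptions not in the document: 0.5% clinically diagnosed CRC per arm by year 5 (half of the planned 1%), silent prevalence s of 0.1% to 0.4% at the 5-year examination, and all silent cancers in Group 1 found.

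p₁ = 0.005 + s; p₂ = 0.005; SE = √{[p₁(1 − p₁) + p₂(1 − p₂)] / 6783}; z = s / SE; chance of a two-sided 5% result favouring the longer interval = Φ(z − 1.96).

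| s | SE (points) | z | Chance |
|---|---|---|---|
| 0.1% | 0.127 | 0.79 | 12% |
| 0.2% | 0.133 | 1.51 | 33% |
| 0.3% | 0.138 | 2.17 | 58% |
| 0.4% | 0.143 | 2.79 | 80% |

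**4. Second illustration, total onset held to the planned rate.** Onset λ = 0.1% per year (1% over 10 years). Assumed: exponential silent phase with mean m = 1 to 5 years, colonoscopy sensitivity 95%, attendance a = 70% or 100%.

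Silent at year 5: S = λm(1 − e^(−5/m)). Clinical by year 5: C = 5λ − S. Group 1 = C + 0.95aS; Group 2 = C.

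| m | a | Group 1 | Group 2 | Difference (points) | Chance |
|---|---|---|---|---|---|
| 1 | 70% | 0.467% | 0.401% | −0.066 | 8.5% |
| 1 | 100% | 0.495% | 0.401% | −0.094 | 13% |
| 2 | 70% | 0.438% | 0.316% | −0.122 | 21% |
| 2 | 100% | 0.491% | 0.316% | −0.174 | 36% |
| 3 | 70% | 0.418% | 0.257% | −0.162 | 37% |
| 3 | 100% | 0.488% | 0.257% | −0.231 | 60% |
| 5 | 70% | 0.394% | 0.184% | −0.210 | 63% |
| 5 | 100% | 0.484% | 0.184% | −0.300 | 86% |

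The largest spurious difference is 0.300 / 0.5 = 60% of the 10-year margin. Every row has the same sign.

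**5. What a 5-year look could say about non-inferiority.** No 5-year margin is stated. Suppose the 0.5-point margin were carried over and the data cut just before the 5-year colonoscopy. The expected difference is then zero, and the chance of meeting the margin with a two-sided 95% interval is Φ(0.005 / SE − 1.96), where SE = √[2r(1 − r) / 6783].
- 5-year risk r = 0.5%: SE = 0.00121, Φ(4.13 − 1.96) = 98.5%.
- r = 0.25%: SE = 0.00086, Φ(5.83 − 1.96) = 99.99%.

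Just after the colonoscopy, every row of step 4 gives more than 99.8%. The strategies have not yet diverged, so meeting the margin carries no information about the 10-year question.

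**The case against.** The strongest reply is that the summary, both design sections and the decision rule all say 10 years, so section 13 is one loosely worded bullet covering three trials. It nowhere announces a by-arm EPoS I comparison or a 5-year non-inferiority claim. That stands, and it limits the point. The sentence still names the primary endpoint and both times, and it exempts no trial. It cannot simply be read as the EPoS II secondary analysis.

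The size is also open to challenge. In step 3, Group 1 reaches 0.6% to 0.9% by year 5 against a planned 1% over ten years, which is high. Step 4 avoids that but relies on sojourn, sensitivity and attendance figures that the protocol does not give. Recruitment over 2 to 3 years means that early recruits may have longer follow-up at the cut. Some Group 2 silent cancers would then have surfaced, which weakens the bias. Only the direction soon after year 5 is established.

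Section 11.1 does allow that fewer cancers could appear under less frequent surveillance, through overdiagnosis. It recognises one detection-related route to this result, though not lead time.

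Three stronger readings are tempting and are not supported:
- A reader might infer that the extra look inflates the type I error of the non-inferiority test. That calculation needs a valid null at year 5, and no 5-year margin exists.
- A reader might infer that the DSMB review lacks a boundary or alpha. These commonly sit in an analysis plan or DSMB charter, which are not shown, and section 14 says that the group was still to be set up.
- A reader might infer that the artefact would stop the trial. The review looks for extreme differences, the expected z values in step 3 are only 0.79 to 2.79, and section 10.2 provides an independent board with a statistician.

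**Conclusion.** The point holds in a limited form. Section 13 contradicts the summary and sections 4.3.1, 4.3.2 and 11.1 on when the primary endpoint is analysed. If followed in EPoS I, it yields a comparison soon after year 5 that is biased in favour of the longer interval.

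The sign rests only on the stated colonoscopy schedule and on the cut falling soon after the 5-year examination. The size is illustrative: a 12% to 80% chance of a nominally significant false advantage in one model, and about 8% to 86% in the other. The ranges are wide because the deciding inputs are not in the document. A 5-year look cannot support non-inferiority in EPoS I.

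The 10-year primary analysis and the sample size are not called into question. In EPoS II both arms are examined at 5 years, so the imbalance described here does not arise there.

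**What to change.** - Amend section 13 so that the primary endpoint is compared by arm and published only after the 10-year examination, in line with the summary and sections 4.3.1, 4.3.2 and 11.1.
- Limit any 5-year EPoS I report to Group 1 yield, safety, attendance and pooled CRC counts, with no between-arm claim on CRC incidence.
- Keep the EPoS II 5-year analysis as the secondary analysis already described, with no non-inferiority claim.
- Add to section 14 that the 5-year DSMB review is confidential and that, for EPoS I, total CRC by arm must be interpreted in light of the one-sided examination. Replacing total CRC with symptom-detected CRC would not remove the problem, because the 5-year examination takes cases out of that count in Group 1.

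The cost is a short protocol amendment and one fewer by-arm paper at 5 years. The group sizes of 6,783 and 6,852 do not change.
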